The SF-12 is a short form health survey containing 12 questions on functional health and well-being and mental health. It has proven useful in surveys of general and specific populations, comparing the relative burden of diseases and differentiating the health benefits produced by a wide range of different treatments. The SF-12 will therefore allow comparison of CSII and MDI participants to each other, and in relation to the general population using data from available literature.

EQ5D

The EQ5D is a standardised instrument for use when measuring health in terms of quality adjusted life years (QALYs). It is used to build a composite picture of the participants health status through a combination of assessment in general health outcomes and state of health on that day.

The SF-12 and EQ5D will also be used by the health economists to derive health economic data.

Fear of hypoglycaemia

The Hypoglycaemia Fear Scale (HFS) (32) is a well validated psychometric tool assessing participants fear of hypoglycaemia both overall and in terms of behaviour and worry. It has been used to assess the impacts of different hypoglycaemic events such as severe, moderate and mild hypoglycaemic episodes on fear of hypoglycaemia (33). A specific benefit to the HFS is that it may be able to identify participants who are likely to maintain high blood glucose levels, thus aiding understanding of potential reasons for poor glycaemic control.

Diabetes Treatment Satisfaction

The Diabetes Treatment Satisfaction Questionnaire (DTSQ) (34) has proven to be highly sensitive in clinical trials (35, 36). It measures treatment satisfaction which refers to an individual's subjective appraisal of their experience of treatment, including ease of use, side effects and efficacy. Improvements in satisfaction are not necessarily accompanied by improvements in QoL; treatment satisfaction can be high despite diabetes having a negative impact on QoL, which is why it is important to measure both separately.

Emotional Wellbeing

The Hospital Anxiety and Depression Scale (HADS) measures anxiety on one subscale and depression on another through the use of 7 questions for each characteristic. It is important to measure emotional wellbeing in the trial as participants may find it easier to manage their condition after DAFNE education or with one of the treatments. This might have a substantial effect on their emotional wellbeing that the QoL measures are not sensitive enough to pick up.

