- 4. Where it has not been possible for a participant to attend their follow up visit, attempts will be made by the educator to collect appropriate data from the participant over the phone, and/or to obtain the relevant data from the participant's medical records.
- 5. Where the participant completed psychosocial questionnaire has not been returned, a second questionnaire will be posted to the participant with a pre-paid reply envelope.

6.To make it easier for participants that do not live locally and/or where it is difficult for the participant to attend the hospital, appropriate research staff (e.g. research nurse, educator, PI) may offer the participant the opportunity to visit them in their home or at an alternative NHS location to carry out data collection.

Lost to Follow-Up

Participants will be considered lost to follow up if they fail to attend for a baseline visit followed by 2 texts and 2 phone calls or if they fail to attend 2 follow-up visits, including the 24 month visit.

Quantitative Psychosocial Procedures for Data Coding

Once the quantitative data has been input into the database, the quantitative psychosocial researcher will have access to this data directly from the database. The data will be extracted and analysed in SPSS version 17. All questionnaires will be coded according to the validated instructions. Data cleaning will take place (removing

any inadmissible entries such as responses outside the stated range i.e. if the response is a scale of 1-5, then any number above 5 or below 1 will be deleted and treated as missing data) and through checking data entry of 10% of data entered. A quality assurance check will also be completed with identification of any outliers in the data. Outliers will remain in the dataset but will be specifically analysed to determine impact on normal distribution. All data will be subject to a 10% quality assurance data entry check and missing data will be treated at such, with analysis conducted on existing data only.

Qualitative Psychosocial Data Collection & Analysis Procedures

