Linear models of insulin usage, body weight, lipids and proteinuria will also be analysed at 2 years with baseline measures as covariates. We will use Poisson regression (or a zero-inflated Poisson regression if necessary) on the number of hypoglycaemic episodes in 2 years, which should also have more power than an analysis based on dichotomy of having experienced/not experienced an episode. Again, GEE will be used for these analyses to account for clustering.

Subgroup Analyses

The analyses outlined above will also be completed for sub-groups stratified at baseline by participants with HbA1c level < and \geq 7.5% (58mmol/mol).

Primarily data will be analysed with missing data excluded. A secondary analysis will also be included using multiple imputation.

Quantitative Psychosocial Analysis

All variables will be subject to statistical analysis. Descriptive and inferential statistical analysis will be conducted using T-tests and ANOVA to compare means, crosstabs to explore individual variables, non-parametric tests including chi-square, correlational analysis and possibly multiple regression analysis. Statistical significance will be defined as $p \le 0.05$ with 95% confidence intervals.

Primarily data will be analysed with missing data excluded. Secondary analyses will also be completed with a) a mean score for each missing questionnaire and b) a minimum score for each missing questionnaire.

A full Statistical Analysis Plan will be submitted at a later date in order to detail this section of the protocol.

10. Trial Supervision

Three committees are being established to govern the conduct of the study:

- 1. Trial Management Group (TMG)
- Trial Steering Committee (TSC)
 Data Monitoring and Ethics Committee (DMEC)

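### In the secondary psychosocial analyses, filling missing questionnaires with a mean score distorts inference, and filling with the minimum is a best case on some scales and a worst case on others

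*Protocol*

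**What the plan says.** Protocol section 9, Quantitative Psychosocial Analysis, sets the main rule: "Primarily data will be analysed with missing data excluded". Section 8, Quantitative Psychosocial Procedures for Data Coding, is in line with it: "missing data will be treated at such, with analysis conducted on existing data only".

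Section 9 then adds two single-value fills: "Secondary analyses will also be completed with a) a mean score for each missing questionnaire and b) a minimum score for each missing questionnaire". It does not say whether the mean is the participant's, the arm's or the overall mean. It does not say whether the minimum is the lowest attainable or the lowest observed score, and it makes no allowance for scales on which a low score is favourable. The planned tests are ordinary ones: "Descriptive and inferential statistical analysis will be conducted using T-tests and ANOVA to compare means", with significance at p ≤ 0.05 and 95% confidence intervals.

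The scales differ in what they measure (section 4). The HADS "measures anxiety on one subscale and depression on another". The Hypoglycaemia Fear Scale (HFS) is a "well validated psychometric tool assessing participants fear of hypoglycaemia". The DTSQ measures satisfaction with treatment.

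For other outcomes the protocol chooses a different method. Section 9 specifies multiple imputation as a secondary analysis of the clinical outcomes (stated at the end of Subgroup Analyses). Section 8, Health Economic Data Collection and Analysis Procedures, specifies it for the within-trial economic analysis.

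**The concern.** A secondary missing-data analysis should show whether the conclusion survives a different, plausible assumption about the people who did not reply. Neither fill does this.

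- **Mean fill.** A t-test or ANOVA cannot tell filled values from real ones. The filled values add to the sample size and contribute no spread.
- **Minimum fill.** One undirected rule covers scales that run in opposite directions. The questionnaires are issued together as a pack (section 8, Table 1). A participant who returns no pack would be scored as least satisfied and also as least anxious, least depressed and least fearful. No single view of non-response produces that profile.

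EQ-5D and SF-12 sit in the same pack and also feed the economic analysis. A missing EQ-5D could therefore be multiply imputed in one analysis and set to a mean or a minimum in another.

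What is at stake is the reading of the robustness checks on fear of hypoglycaemia, treatment satisfaction and emotional wellbeing, all of which are named endpoints in section 3.

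**Working it through.** The protocol gives no error rate, power or expected return rate for the questionnaires, so there is no figure of its own to reproduce. The effect of each rule is computed directly.

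**Inputs**
- Missing share f: assumed. The only guides are the 10% drop-out in section 9, Sample Size, and the 10% and 15% scenarios in the August 2012 review. Values of 20% and 30% are shown for range.
- Arm size n = 140 (Trial Summary), used in the simulation.
- Distance d of a scale's mean above its minimum, in SD units: assumed, 1 to 3.
- Direction of HADS, HFS and DTSQ: inferred from what each measures, since the protocol does not state it.

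**Mean fill, standard error**
- Complete-case SE of an arm mean: s / √(n(1 − f)).
- After the fill, the variance is about (1 − f)s² over n values, so the SE is s√(1 − f) / √n.
- Ratio of the two: (1 − f).

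**Mean fill with arm means.** Each arm's mean is unchanged, so the estimated difference equals the complete-case difference and only the SE shrinks. Type I error ≈ 2[1 − Φ(1.96(1 − f))]. Simulation used 5,000 runs with data missing completely at random.

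| f | SE ratio | Type I, formula | Type I, simulated | Complete case, simulated |
|---|---|---|---|---|
| 10% | 0.90 | 7.8% | 8.5% | 5.3% |
| 15% | 0.85 | 9.6% | not run | not run |
| 20% | 0.80 | 11.7% | 11.1% | 4.7% |
| 30% | 0.70 | 17.0% | 16.6% | 4.7% |

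**Mean fill with one overall mean.** With equal missingness the difference is also multiplied by (1 − f), so difference and SE shrink together. Simulated type I error is 5.3%, 4.7% and 4.7% at 10%, 20% and 30% missing. A true effect is reported at about 0.90 of its size at 10% missing and 0.85 at 15%.

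**Minimum fill, standard error.** The variance after the fill is (1 − f)s² + f(1 − f)d². With d in SD units, the SE ratio to complete case is (1 − f)√(1 + f·d²).

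| f | d = 1 | d = 1.5 | d = 2 | d = 3 |
|---|---|---|---|---|
| 10% | 0.94 | 1.00 | 1.07 | 1.24 |
| 20% | 0.88 | 0.96 | 1.07 | 1.34 |

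The SE may fall or rise, so shrinkage is certain only for the mean fill.

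**Minimum fill, bias between arms.** An arm with true mean d above the minimum has a filled mean of (1 − f)d above it. With no true difference and missing shares f₁ and f₂, the filled means differ by (f₂ − f₁)d, and the arm with more missing forms scores lower.
- 10-point difference: 0.10 × 1 = 0.10 SD to 0.10 × 2 = 0.20 SD.
- 20-point difference: 0.20 × 1 = 0.20 SD to 0.20 × 2 = 0.40 SD.

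On HADS and HFS a lower score reads as benefit, so the bias favours the arm with more non-responders. On the DTSQ the same rule counts against that arm.

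**The case against.** The strongest reply is that these are secondary analyses of endpoints that section 3 lists as ancillary. The main psychosocial analysis leaves missing data out, and the HbA1c result is untouched. That stands, and it limits the damage to the robustness checks.

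A second reply is that section 9 promises a full statistical analysis plan, the usual place to say which mean is meant and how each scale is scored. This stands in part. The type of mean and the scale directions can be settled there. The choice of single-value fills, however, is already fixed in the protocol.

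Third, the figures depend on assumptions. The type I inflation needs arm means. If a participant's own mean from other visits were meant, neither calculation for the mean fill would apply as it stands. The between-arm bias needs unequal missingness, for which the protocol gives no rates.

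A reader might infer three stronger points that the documents do not support:

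- **That sections 8 and 9 contradict each other.** The restriction to existing data in section 8 closes a paragraph on data cleaning and matches the main rule in section 9. Adding secondary analyses to a main rule is not a conflict.
- **That both fills shrink the standard error.** The minimum fill can widen it, as the table shows.
- **That the type I error is worse still once clustering by course is added.** That is a separate matter from imputation, and the ICC of 0.05 in section 9 belongs to the HbA1c calculation. No ICC is given for the questionnaires.

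**Conclusion.** The point holds for the two secondary analyses and goes no further.

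The mean fill is unsuitable under either reading examined. With arm means it repeats the complete-case difference with an SE of 0.90 (10% missing) or 0.85 (15%) of the complete-case value, and the type I error is about 8% or 10%. With one overall mean the error rate is kept but the effect is pulled toward zero.

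The minimum fill is neither a worst case nor a best case across the set of scales. At an assumed 10-point difference in missingness it creates a spurious 0.10 to 0.20 SD, in favour of the arm with more non-responders on HADS and HFS. This rests on a mean 1 to 2 SD above the minimum, on the minimum being the value actually filled in, and on direction inferred from the constructs. To call it the best possible score for non-responders also assumes that the lowest attainable score is meant, which the protocol does not say.

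Severity is low to moderate: the checks as written cannot show robustness, but the main results do not depend on them.

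**What to change.** Replace both fills in section 9, Quantitative Psychosocial Analysis, with multiple imputation, as the protocol already does for the clinical and economic outcomes. The imputation model should include at least arm, site, course, and baseline and earlier scores.

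If an extreme-case analysis is kept, define it scale by scale. State each scale's scoring direction and fill in the unfavourable end: the maximum on HADS and HFS, and the minimum on satisfaction scales, if the scoring manuals confirm the inferred directions. Letting the filled value differ between arms would show how far unequal non-response could move the comparison.

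Section 8 needs no change on this account. The cost is a short wording change and routine programming, with no new data.
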